#### **4.3 Reproductive Potential and Pregnancy Avoidance**

Sexually active females of childbearing potential (FOCP) must agree to use an acceptable form of contraception. FOCP will be advised to use acceptable contraceptives from the time of signing the Informed Consent Form (ICF) and for at least 3 months following the administration of the IP. If hormonal contraceptives are used they should be administered according to the package insert, in addition to use of an approved barrier method. FOCP who are not currently sexually active must agree to use acceptable contraception, as defined below, if they become sexually active during the study period.

Male subjects with reproductive potential agree to comply with approved double barrier contraceptive method from time of signing the ICF and for 3 months after IP administration. In addition, they must be advised to not donate sperm during this period.

An acceptable method of contraception is defined as one that has no higher than a 1% failure rate. In this study, the only acceptable methods of contraception are:

Condoms used with the following acceptable contraceptives:

- IUDs
- Hormonal contraceptives (oral, depot, patch, injectable, or vaginal ring)

Other acceptable double barrier contraceptive methods are:

- Double barrier methods (e.g., condoms and diaphragms with spermicidal gel or foam)
- Male condom PLUS spermicide
- Cap (plus spermicidal cream or jelly) PLUS male condom and spermicide

- Diaphragm (plus spermicidal cream or jelly) PLUS male condom and spermicide
- Copper T PLUS condom or spermicide.

#### 4.4 Restrictions

Subjects should comply with the following restrictions after intratympanic injection.

- Prevent water exposure (e.g., shower spray) or submersion (e.g., swimming, bathing) of the injected ear, until cleared by follow-up otology examination to confirm closure of the TM opening. Subjects will be instructed on how to completely cover the Index Ear to enable showering until cleared.
- Abstain from heavy physical exertion for 24 hours following injection.
- No insertion of cotton-tipped applicators into the external ear canal of either ear until cleared by follow-up otology examination to confirm closure of the TM opening.
- No use of an occluding ear mold hearing aid in the Index Ear for 3 days following injection.

#### 4.5 Withdrawal of Subjects

A subject may withdraw from the study at any time for any reason without prejudice to their future medical care; however, prior to randomization, it should be made clear to potential subjects that early withdrawal from the study including loss to follow up may pose some risk to the subject and can be damaging to the scientific research. Once a subject has been randomized, the Investigator will make every reasonable effort to keep the subject in the study.

The Investigator or Sponsor may withdraw the subject at any time during the study in the interest of subject safety. In such cases, the withdrawal of a subject by the Investigator should be discussed whenever possible with the Medical Monitor.

After study drug administration, subjects should continue to be followed through completion of the study unless a subject withdraws consent or is lost to follow up.

Regardless of the reason(s) for early termination of a subject, final evaluations are to be performed as completely as possible. Comments (spontaneous or elicited) or complaints made by the subject, the reason for termination, date of withdrawal, and the total amount of IP administered must be documented.

Subjects who discontinue prior to the Day 30 assessment for a reason other than an AE may be replaced and randomized to the same treatment assignment. Subjects who discontinue after Day 30 will not be replaced.

##### 4.5.1 Reasons for Subject Discontinuation

Reasons for subject discontinuation include, but are not limited to:

- Adverse event: A subject may be discontinued from study due to AE only from the time of randomization (official study entry) until the time of IP administration. If a subject experiences an AE after the single dose IP administration, the subject should continue to be followed in the study and would only discontinue prematurely if the subject withdraws consent or is lost to follow up.
- Protocol violation or subject non-compliance.
- Subject withdrawal of consent: A subject should be considered to have withdrawn consent when the subject no longer wishes to participate in any aspect of the study, and does not want any further assessments, visits, or contact. A subject's refusal to participate in specific aspects of the study, such as a refusal to continue to provide blood samples, will NOT constitute withdrawal of consent. Investigators should make every effort to facilitate the subject's continued participation in remaining aspects of the study.
- Lost to follow-up: A subject will not be considered lost to follow-up until the end of the 12-week follow up period and after all efforts to contact the subject have been exhausted. At least 3 documented attempts must be made to contact any subject lost to follow-up at any time point prior to the last scheduled contact (office visit or telephone contact). One of these documented attempts must include a written communication sent to the subject's last known address via courier or mail (with an acknowledgement of receipt request) asking that they return to the site for final safety evaluations.

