## Footnotes:

a Subjects who receive study drug and withdraw or are withdrawn from the study early will be requested to complete early termination procedures outlined under Day 90.

b Otological examination will assess the following under direct magnification: external ear, external auditory canal, TM and TM mobility. The otological examinations will be conducted by the unblinded otologist who performs the intratympanic injection and also conducts all post-injection otological examinations through at least Day 30 and preferably throughout the study.

c Vital signs (i.e., blood pressure, pulse rate, respiratory rate, and temperature) will be recorded after subject is at rest in a seated or supine position for at least 5 minutes.

d On Day 0, vital signs will be conducted pre-dose, 30 ( $\pm 5$ ) minutes post-dose, and 4 hours ( $\pm 15$  minutes) post-dose.

e ECG will be recorded after subject is at rest in a supine position for at least 5 minutes.

f On Day 0, ECG will only be conducted at 4 hours ( $\pm 15$  minutes) post-dose.

g FSH level will be obtained on post-menopausal women only (defined as continuous amenorrhea of at least 12 months and not surgically sterile).

h Only female subjects of childbearing potential will require a negative serum pregnancy test at Screening and negative urine pregnancy test prior to randomization at Day 0. Female subjects of childbearing potential will also require a urine pregnancy test at Completion or Early Termination.

i On Day 0, hematology and chemistry lab samples will be collected prior to dosing but do not have to be analyzed prior to dose.

j On Day 0, PK samples will be collected pre-dose and 4 hours ( $\pm 15$  minutes) post-dose.

k The intratympanic injection will be performed by an unblinded otologist who will also conduct all post-injection otological examinations through at least Day 30 and preferably throughout the study.

l Ultra-high frequency audiogram testing [10,000-16,000 Hz] will be performed if available based on site audiometer specifications.

m Sound field binaural testing using a single 0° azimuth loudspeaker.

Approved

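### Protocol 4.5 and 4.5.1 conflict on whether a dosed subject can be withdrawn because of an AE; followed literally, 4.5.1 removes AE as a discontinuation reason for every dosed subject

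*Protocol*

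**What the plan says.** Protocol 4.5, paragraph 2, gives a general power: "The Investigator or Sponsor may withdraw the subject at any time during the study in the interest of subject safety". Paragraph 3 of the same section says that, once dosed, "subjects should continue to be followed through completion of the study unless a subject withdraws consent or is lost to follow up".

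Protocol 4.5.1 then sets a specific rule for AEs: "A subject may be discontinued from study due to AE only from the time of randomization (official study entry) until the time of IP administration". A subject who has an AE after the single dose stays in follow-up and "would only discontinue prematurely if the subject withdraws consent or is lost to follow up". The list that contains this rule is open: "Reasons for subject discontinuation include, but are not limited to".

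On recording, 4.5 requires that "the reason for termination, date of withdrawal, and the total amount of IP administered must be documented". Section 7.1.4 also requires the reason in the source document and eCRF, and an End of Study eCRF page for every subject who received study medication.

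On replacement, 4.5 says "Subjects who discontinue prior to the Day 30 assessment for a reason other than an AE may be replaced", with randomization to the same arm.

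Two planned outputs use this information. Section 9.5 tabulates discontinuation reasons by treatment group, and 9.8 summarizes or lists the AEs that led to withdrawal.

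**The concern.** Sites have two instructions that cannot both be followed for a dosed subject whose AE makes the Investigator or Sponsor want to withdraw that subject for safety. It does not help to distinguish stopping treatment from leaving the study. After a single injection there is no treatment left to stop, and 4.5.1 speaks of leaving the study.

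Tolerability is part of the primary objective, and the 9.5 reasons table is where a reader would look for AE-driven exits by arm. If 4.5.1 is followed literally, a zero in the AE row for dosed subjects is fixed in advance by the rule and is not an observation. The same coding may also decide whether a subject who left because of an AE can be replaced, which would add a dosed subject to the arm.

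**Working it through.** **1. The AE window in 4.5.1.** It opens at randomization and closes at dosing. Section 6.3.3 puts both on Day 0, so the window is part of one day.

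**2. Who can leave inside it.** Only a subject who has been randomized but not dosed. Under 9.4 the Safety Analysis Set requires dosing, so that subject is outside it but inside the Randomized Set.

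**3. Result for the 9.5 table.** Section 9.5 covers each analysis set. Under 4.5.1 taken literally, the AE row is zero for dosed subjects. In the Randomized Set it can still be above zero, through pre-dose exits on Day 0.

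**4. Exit routes after dosing for a subject with an AE.** Section 4.5.1 leaves two: consent withdrawal and loss to follow-up. It also says that loss to follow-up is not declared until the 12-week follow-up has ended. Before Day 30, consent withdrawal is therefore the only one of the two that can be recorded.

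**5. Result for replacement.** The rule in 4.5 excludes AE exits before Day 30. There are two cases:
- If the coded reason governs, a dosed subject who withdraws consent because of an AE is coded as a non-AE exit and may be replaced. The AE exception then reaches only pre-dose exits.
- If the underlying reason governs, that subject may not be replaced.

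The documents do not say which applies.

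**6. Denominators.** Section 6.3.3 allocates the two sentinel subjects 1:1 and the rest 17:5. This gives 1 + 17 = 18 on PIPE-505 and 1 + 5 = 6 on placebo, total 24, ratio 18/6 = 3. It reproduces the planned 18:6. The plan has no power figure to reproduce here, because it states that the sample size is not statistically based.

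**7. Size of one exit**, assuming all planned subjects are dosed:

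| Arm | AE recorded as reason, no replacement | Coded otherwise, no replacement | Coded otherwise and replaced |
|---|---|---|---|
| PIPE-505 | 1/18 = 5.6% | 0/18 | 0/(18 + 1) = 0/19 |
| Placebo | 1/6 = 16.7% | 0/6 | 0/(6 + 1) = 0/7 |

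Each such exit therefore moves the row by 5.6 points on PIPE-505 or 16.7 points on placebo. These figures show what one hypothetical exit does. They do not predict how many there will be.

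**The case against.** The strongest reply is that 4.5.1 is a retention rule and not a coding rule. It keeps dosed subjects in safety follow-up, and paragraph 3 of 4.5 says the same. The specific rule can be read as overriding the general safety power, and a safety withdrawal need not be for a post-dose AE. The list of reasons is open and the reason must be documented, so a site could still enter the AE. On a plain reading, someone who withdraws consent because of an AE has left because of an AE and may not be replaced.

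Much of this stands, and it makes the consequences conditional: the zero depends on following 4.5.1 literally, and replacement depends on the coded reason governing. It does not remove the conflict. Nothing supplied says that the specific rule prevails, or how to code an AE-driven exit whose formal route is consent withdrawal.

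The public SAP copy does not show its disposition text, the table shells are in a separate file, and protocol 9.3 lets the SAP supersede the protocol. The sponsor may therefore have settled the coding there.

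A reader might go further in four ways that the documents do not support:
- **The whole 9.5 table must show zero AE discontinuations.** It need not, because the Randomized Set can include pre-dose AE exits.
- **Footnote a of the Schedule of Events is part of the contradiction**, since it refers to "Subjects who receive study drug and withdraw or are withdrawn from the study early". It is not: 4.5.1 also lists protocol violation or non-compliance with no time limit, so a dosed subject can be withdrawn without touching the AE rule.
- **The 9.8 output must be empty.** That follows only if it is drawn from the discontinuation reason. A flag on the AE form could fill it, and the supplied text does not name the source.
- **AEs would be under-counted.** They would not. A dosed subject's recorded AEs stay in the Safety Analysis Set whatever exit reason is entered.

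**Conclusion.** The concern holds in a limited form. Paragraph 2 of 4.5 conflicts with 4.5.1 and with paragraph 3 of 4.5. Followed literally, 4.5.1 removes AE as a discontinuation reason for every dosed subject in the 9.5 table. If the coded reason also governs replacement, the AE exception in 4.5 reaches no dosed subject. Before Day 30 that can happen only through consent withdrawal.

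The effect is confined to descriptive disposition, to who may be replaced, and possibly to the 9.8 withdrawal output. The primary endpoint does not change. In a study this small one exit is still visible in the row, and the correction is cheap, so it should be made. Confidence is medium, because the SAP disposition text, the shells and the eCRF pages could not be seen.

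**What to change.** 1. Reconcile 4.5 and 4.5.1 so that sites have one instruction on withdrawing a dosed subject because of an AE. This point takes no view on which withdrawal rule is right.
2. On the End of Study eCRF page already required for every dosed subject, record whether an AE was the underlying reason for leaving, whatever the formal route, unless such a field already exists.
3. Use that field for the 9.5 reasons table and for the 4.5 replacement rule. Use it also for the 9.8 output of AEs that led to withdrawal, unless the SAP or shells already name another source.

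The cost is a wording change in two sections and at most one field on an existing page. The downside for the sponsor is that AE-related exits may be reported above zero and fewer dropouts can be replaced.

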#### 4.6 Early Termination of Study/Closure of Site

The study may be terminated early if new toxicological findings or results affecting the safety of the subjects become available. The Sponsor reserves the right to terminate the study at any time for any reason.

The Sponsor may terminate a study site at any time for any reason, including inadequate subject recruitment, Good Clinical Practice (GCP) non-compliance, poor quality data, evidence of attempted or proven fraud, or for any reason at the Sponsor's discretion.

In the event the Sponsor terminates a particular study site prior to the end of the trial, the site staff is responsible for notifying the Institutional Review Board (IRB).

## 5. PRIOR AND CONCOMITANT TREATMENT

### 5.1 Prior Treatment

Prior treatment includes all treatment (including herbal treatments, vitamins, non-pharmacological treatment such as psychotherapy as appropriate) received within 30 days of signing the ICF. Prior treatment information must be recorded on the appropriate case report form (CRF) page.

### 5.2 Concomitant Treatment

Concomitant treatment taken from the date of signing the ICF through the 90-day follow-up visit will be listed on the appropriate CRF page.

Approved

## 6. INVESTIGATIONAL PRODUCT

Refer to the PTI-505-101 Pharmacy Manual for further details regarding handling of the IPs in this study.

### 6.1 Description of Investigational Product

[REDACTED]

[REDACTED]

Additional information is provided in the IB and the Pharmacy Manual.

### 6.2 Randomization Code Generation and Storage

The randomization schedule will be generated by the Sponsor or designee and loaded to the Interactive Voice/Web Response System (IxRS) prior to the start of the study.

[REDACTED]

## 6.3 Administration of Investigational Product(s)

### 6.3.1 Index Ear Selection and Dosing Procedure

The IP or Placebo will be administered by an intratympanic injection as an out-patient procedure by a qualified otologist or neuro-otologist. The ear selected for dosing (i.e., the Index Ear) will be identified based on the audiometry and QuickSIN results at Screening as follows:

- The ear with the worse audiometry, as determined by the PI, will be identified as the Index Ear.
- If both ears are equal by audiometry, the ear with the highest SNR on the QuickSIN will be defined as the Index Ear.
- If the audiometry and QuickSIN are equal in each ear, the PI and subject will determine the Index Ear.

Otoscopy of the Index Ear canal and TM will be performed prior to administration and excessive earwax or debris will be manually cleared. At the discretion of the otologist or neuro-otologist performing the intra-tympanic injection, a topical anesthetic (e.g., EMLA cream [eutectic lidocaine/prilocaine mixture] or xylocaine [4% lidocaine solution or 10% pump spray]) may be applied to the external tympanic membrane. Given the transient discomfort associated with topical anesthesia and the extremely small gauge of the needle used for injection, the Investigator may also elect to perform the intra-tympanic injection without use of a topical anesthetic, after discussion with the subject. If applied, any remaining anesthetic in the external canal will be suctioned off prior to the injection in order to avoid spillage into the tympanic cavity and possible vertigo or dizziness. Any local anesthetic, if utilized, should be recorded in the subject's source record and the Concomitant Medications case report form.

The injection will be performed under otomicroscopy following standard transtympanic procedural technique, and with the subject reclining at an angle of up to 30° on the examination table or chair. The subject's head will be tilted 45° towards the unaffected ear during the injection and for 10 minutes following the administration. This will allow the round window niche and membrane to be at the lowest point of the tympanic cavity, facilitating the IP to collect in the round window niche and have direct contact with the round window membrane. The injection will be performed using a 1mL luer-lock syringe with a 3.5-inch 25-27-gauge needle (gauge based on Investigator preference). The posterior inferior quadrant of the TM will be punctured with the injection needle of choice, and the 200 microliters of either the PIPE-505 Suspension or Diluent alone (Placebo) will be delivered to the tympanic cavity over 5-10 seconds. The Investigator will maintain visualization of the needle bevel past the TM opening to avoid contact with the round window and other critical middle ear structures.

Subjects will remain in this position for approximately 10 minutes in order to avoid early loss of medication into the nasopharynx through the Eustachian tube. In addition, subjects will be asked to refrain from excessive swallowing, yawning, or speech for 30 minutes following the injection. After 30 minutes, the subject will have no restriction on activity, with the exception of restrictions outlined in Section 4.4.

### 6.3.2 Blinding the Treatment Assignment

Study drug supplies will be provided to sites as follows:

Open-label vials of Diluent for PIPE-505 Suspension (also administered alone as Placebo) will be provided in bulk format to be stored at 2-8 °C. An open-label Diluent vial will be utilized for each dose administration, whether mixed with the Active Ingredient or given alone as Placebo.

Identical appearing study drug kits will be supplied to sites and stored at controlled room temperature. Each kit will contain either an open-label vial of PIPE-505 Active Ingredient, or sham contents to mimic the weight of a vial of Active Ingredient. Kits will be labeled with a unique kit number to be assigned to subjects as they are randomized via the IxRS system for dosing. Although the trained pharmacist or nurse (i.e., dose preparer) preparing the study drug dose for administration is unblinded, the identical appearing blinded kits are utilized to prevent unblinding of blinded study staff who may have general access to the study drug storage areas.

An unblinded dose preparer will:

- Be responsible for preparing the study dose of PIPE-505 or Placebo according to the randomization assignment (kit number) obtained through the IxRS
- Deliver the preloaded syringe to the unblinded otologist or neuro-otologist responsible for administering the dose to the subject. The preloaded syringe will be covered to prevent content visualization by any other person (other than the responsible person performing the injection) Be identified on the site delegation of responsibility log as the unblinded dose preparer
- Be restricted from participating in any subject assessment
- Be restricted from disclosing treatment assignments to any study staff, with the exception outlined in Section 6.3.4

The Placebo formulation will consist of the thermosensitive gel (Poloxamer 407) alone. Due to formulation steps, as well as the clear color of the gel alone in comparison to the opacity of the PIPE-505 Suspension, the otologist performing the intratympanic injection cannot be masked from subject's assignment.

An unblinded otologist/neuro-otologist is responsible for study drug administration. The unblinded otologist or neuro-otologist is permitted to perform and/or interpret safety assessments including vital signs, electrocardiograms (ECG), clinical laboratory test results (routine hematology, chemistry and urinalysis), physical and otological examinations and AEs/SAEs as described in Section 8, Adverse and Serious Adverse Events Assessment. The unblinded otologist/neuro-otologist is prohibited from conducting audiology, distortion product optoacoustic emission, auditory brainstem responses, electrocochleography (ECochG), middle ear muscle reflex, Speech Spatial Qualities of Hearing Scale, Word Recognition Score (WRS), Speech Recognition Threshold (SRT), Quick Sentences-in-Noise (QuickSIN), and Words-in-Noise (WIN).

The subject, all assessors responsible for evaluating the subjects or interpreting data obtained through these assessments, and other team members will remain blinded to subject assignment for the entire study duration (i.e., through database lock) with the exceptions of the dose preparer and otologist/neuro-otologist who administers study drug. The subject will be prevented from

visualizing the formulation during the procedure. All other Investigators and assessors will be blinded.

